Dept. of Hematology T: [contact] [name] Email: [contact]

Coordinating Center

Data Coordinating Center

City of Hope National Medical Center

Email: [contact]

PROTOCOL TEAM

Biostatistician

[name]

City of Hope National Medical Center

Dept. of Computational and Quantitative Medicine T: [contact] [name] Email: [contact]

Protocol Development Scientist

[name]

City of Hope National Medical Center

Dept. of Hematology T: [contact] [name] Email: [contact]

Participating non-COH sites

Site Lead Investigator

[name] Stanford University Dept. of Medicine

Email: [contact]

Site Lead Investigator

[name]
Dana-Farber Cancer Institute
Dept. of Medical Oncology
Email: [contact]

Site Lead Investigator

[name] Emory University Dept. of Hematology and Medical

Oncology

Email: [contact]

[figure not shown]
Site Lead Investigator

[name] Memorial Sloan Kettering Cancer Center Dept. of Medicine

Dept. of Medicine T: [contact]

Email: [contact]

STUDY SCHEMA

^{*} At the treating physician's discretion

[†] Patients in CR may receive a 3rd cycle of PolaR-ICE at the treating physician's discretion

PROTOCOL SYNOPSIS

Protocol Title

A Phase 2 Study of Polatuzumab Vedotin with Rituximab, Ifosfamide, Carboplatin, and Etoposide (PolaR-ICE) as Initial Salvage Therapy for Relapsed/Refractory Diffuse Large B-cell Lymphoma

Study Detail		
Population/Indication(s):	Relapsed/Refractory Diffuse Large B-cell Lymphoma	
Phase:	2	
Sample Size:	Expected: 40 evaluable patients; Maximum: 53 patients	
Estimated Accrual Duration:	24 months	
Estimated Study Duration	~ 4 years	
Participant Duration:	~ 24 months	
Participating Sites:	 City of Hope Duarte, CA Stanford University Dana-Farber Cancer Institute 	
	 Dana-Farber Cancer Institute Emory University Memorial Sloan Kettering Cancer Center 	
Study Agents:	Polatuzumab vedotin, Rituximab, Ifosfamide, Carboplatin, Etoposide	
Sponsor:	City of Hope	
Industry Partner:	Genentech	

Rationale for this Study

Novel treatment strategies are needed to improve outcomes for relapsed/refractory (R/R), transplant-eligible DLBCL patients, where the goal is to achieve a high-quality remission that enables subsequent ASCT. The primary unmet need is the failure to achieve a high rate of CR, as achievement of a PET-negative CR following second-line salvage therapy has been associated with improvement in outcome in relapsed DLBCL patients who proceed to ASCT.[1-3] Pola is a potent anti-CD79b ADC with demonstrated anti-tumor efficacy in R/R DLBCL and has been combined safely with chemotherapy resulting in higher response rates compared to chemotherapy alone.[4] Notably, Pola combined with BR in a population of heavily treated patients also resulted in improved PFS and OS compared to BR alone. Therefore, it has been demonstrated that Pola combined with chemotherapy can improve outcomes in patients with DLBCL. An important observation about the clinical use of Pola is that peripheral neuropathy has limited the therapeutic index of the drug, with the ultimate dose of the drug being 1.8 mg/kg as opposed to the 2.4 mg/kg dose initially chosen as the recommended phase 2 dose. In addition, the duration of Pola dosing has been limited to 6 doses, prior to the onset of dose-limiting neuropathy. Therefore, the ideal dosing of Pola may be as a short course to improve upon the efficacy of combination chemotherapy, as demonstrated with bendamustine and CHOP in other studies. With the need for more effective bridging therapy prior to ASCT in R-R DLBCL, there is an ideal opportunity to utilize Pola as part of salvage therapy to increase the CR rate prior to ASCT. The CR rate prior to transplant is an important prognostic factor for ASCT outcome; therefore, our hypothesis is that improving salvage therapy with Pola may increase the durable response rate with a salvage/ASCT approach.

In addition, it has been demonstrated in Hodgkin lymphoma that the use of an effective ADC (brentuximab vedotin) after ASCT can improve progression-free survival. The AETHERA trial demonstrated that brentuximab vedotin consolidation treatment following ASCT prolongs PFS in patients with high risk relapsed or refractory classical Hodgkin lymphoma compared to placebo.[5] Like brentuximab vedotin in R/R Hodgkin lymphoma, Pola is an ADC that has potent anti-tumor activity in patients with R/R DLBCL. Pola has already been associated with improved survival in patients with R/R DLBCL receiving chemotherapy as compared to chemotherapy alone.[6] Therefore, we propose to use Pola as consolidation therapy after ASCT with the goal of increasing the proportion of patients with durable remission after ASCT.

Objectives

Primary Objectives

- Safety Lead-in: Evaluate the safety and tolerability of polatuzumab vedotin (Pola) added to rituximab, ifosfamide, carboplatin, and etoposide (PolaR-ICE) as first salvage therapy for relapsed or refractory (R/R) diffuse large B-cell lymphoma (DLBCL).
- Phase 2: Evaluate the anti-tumor activity of PolaR-ICE as first salvage therapy for R/R DLBCL as assessed by the complete response rate after 2 cycles.

Secondary Objectives

- Evaluate the overall response rate to PolaR-ICE as first salvage therapy for R/R DLBCL.
- Evaluate the progression-free and overall survival of patients who received PolaR-ICE as first salvage therapy for R/R DLBCL followed by autologous stem cell transplantation (ASCT) and single-agent Pola consolidation after ASCT.
- Evaluate the CR rate after Pola consolidation among those who were PR at ASCT.
- · Evaluate the toxicity of PolaR-ICE salvage therapy and that of Pola consolidation after ASCT.
- Assess the rate of stem cell mobilization and collection failure in patients with R/R DLBCL who receive PolaR-ICE as first salvage therapy.

Exploratory Objectives

- Assess the kinetics of circulating tumor DNA after PolaR-ICE as first salvage therapy for R/R DLBCL followed by ASCT and single-agent Pola consolidation after ASCT.
- Assess possible biomarkers of response to PolaR-ICE in patients with R/R DLBCL.
- Examine the association between clinical outcomes (response, PFS) and pathological tumor characteristics.
- Examine the association between clinical outcomes (response, PFS) and ctDNA characteristics (mutation profile, kinetics of clearance).

Study Design

This is a phase 2 study of PolaR-ICE followed by ASCT and Pola consolidation in patients with relapsed or refractory (R/R) DLBCL. Adult patients with pathologically documented relapsed or refractory DLBCL after induction therapy will be enrolled. Patients with subsets of DLBCL, including mediastinal large B-cell lymphoma, transformed DLBCL, and aggressive B-cell lymphoma unclassified will not be excluded. Patients must have received anthracycline- or anthracenedione-containing induction chemotherapy. The Safety Lead-In will use a design that is slightly modified from the IQ rolling 6 design.[7] Dose level 1 will use the standard doses of R-ICE (rituximab 375 mg/m2, ifosfamide 5000 mg/m2 or 3 x 1670 mg/m2, carboplatin area under the curve 5 mg/mL x min; maximum dose, 750 mg, and etoposide 100 mg/m2 per day for 3 days) with the approved dose of Pola (1.8 mg/kg). There will be a dose de-escalation dose level (dose level -1), only if necessary. Dose level -1 will use the standard doses of R-ICE with a reduced dose of Pola (1.4 mg/kg). The maximum number of PolaR-ICE cycles is 3. Patients who proceed to ASCT directly after PolaR-ICE and have achieved an objective response to PolaR-ICE will receive single-agent Pola consolidation after ASCT at the standard dose of Pola (1.8 mg/kg) every 21 days. The maximum number of Pola-containing cycles of therapy is 6.

After the tolerable dose is confirmed the study will progress to the phase 2 portion of the study, which will employ a twostage design to evaluate the CR rate after 2 cycles of PolaR-ICE. Patients who were enrolled during the safety lead-in portion at the final dose level deemed tolerable for Phase 2 will also be included in the Phase 2 response evaluation if they are evaluable for response.

Evaluation Criteria and Endpoints

Toxicities will be will be graded using the NCI CTCAE v 5.0.

Response/progression will be assessed per 2014 Lugano classification.

Primary Endpoint(s):

- Safety Lead-in: Unacceptable toxicity (defined in Section 11.2) during the first 2 cycles of PolaR-ICE therapy.
- Phase 2: Complete response (CR) rate after 2 cycles of PolaR-ICE therapy.

Secondary Endpoint(s):

- Overall response rate (ORR) at the end of PolaR-ICE therapy.
- · Progression-free survival (PFS) and Overall survival (OS).
- CR rate after Pola consolidation among patients who were PR at ASCT.
- Toxicity of PolaR-ICE salvage therapy and toxicity of Pola consolidation after ASCT.
- · Stem cell mobilization rate and collection failure.

Statistical Considerations

Safety Lead-in:

During the safety lead-in portion of the study, a design that is slightly modified from the IQ rolling 6 design will be used.[7] In this design, up to 8 evaluable patients may be treated at each dose level, and the highest dose level with <33% evaluable patients having unacceptable toxicities will be considered tolerable with respect to unacceptable toxicities. If DL 1 is not tolerable, DL -1 will be explored.

Phase 2:

The Phase 2 portion of the study adopts a two-stage design. Patients who were enrolled during the safety lead-in portion at the final dose level deemed tolerable for Phase 2 will also be included in the Phase 2 response evaluation if they are evaluable for response.

At the first stage, 20 patients will be enrolled. If <8 complete responses are seen, the accrual will be terminated. If at least 8 patients achieve a complete response, the trial will continue to the second stage. At the second stage, 20 additional patients will be entered. At the end of stage 2, if 21 or more patients out of the total 40 patients experience a complete response, the combination will be considered worthy of further study. If <21 patients experience a complete response then no further investigation of the combination is warranted.

The 2-stage design aims to differentiate between the null hypothesis (disappointing rate) of 40% CR rate and an alternative hypothesis (promising rate) of 60% CR rate. The null hypothesis of 40% CR rate is based on a large randomized study comparing R-ICE with R-DHAP (rituximab, dexamethasone, cytarabine, cisplatin) as salvage regimen followed by ASCT for relapsed/refractory DLBCL [8]. Similar complete response rates were observed after 3 cycles of R-ICE (37%, n=197) vs. 3 cycles R-DHAP (40%, n=191). Therefore, we would consider a 40% CR rate a discouraging rate and 60% a promising CR rate for this regimen to merit further study. The design has a 1-sided type I error of 7.3% and a power of 87%. The expected sample size under the null hypothesis is 31.7, and the design has a 42% chance of early termination after Stage I if the true CR rate is 40%.

Abbreviated Eligibility Criteria

Main Inclusion Criteria

- · Age: ≥ 18 years
- ECOG ≤ 2
- Histologically confirmed diagnosis of diffuse large B-cell lymphoma according to the WHO classification, with hematopathology review at the participating institution. Subtypes of DLBCL including transformed indolent lymphomas (TIL), primary mediastinal large B-cell lymphoma (PMBCL), and high-grade B-cell lymphoma not otherwise specified (HGBCL-NOS) are eligible.
- Biopsy-proven relapsed or refractory disease after 1 line of frontline CD20-directed immunotherapy with anthracyclineor anthracenedione-based multi-agent chemotherapy. Monotherapy with rituximab or other CD20-directed

immunotherapy prior to frontline chemotherapy or as maintenance therapy, and radiation therapy in a limited field or as a part of the frontline treatment plan are permitted.

- Prior lymphoma therapy should be completed at least 2 weeks before start of protocol therapy.
- Measurable disease by CT or PET/CT scan with one or more sites of disease ≥ 1.5 cm in longest dimension.
- Considered eligible for high-dose chemotherapy followed by ASCT.
- Fully recovered from the acute toxic effects (except alopecia) to ≤ Grade 1 to prior anti-cancer therapy.
- Be willing to provide archival tissue of a biopsy that was performed after the frontline systemic therapy (if unavailable, exceptions may be granted with Study PI approval).
- · Adequate hematological, renal, and hepatic function.
- Women of childbearing potential: negative urine or serum pregnancy test.
- Agreement to use an effective method of contraception for both women of childbearing potential and male patients
 during the study and through at least 12 months post-last dose of pola or rituximab for women, 5 months post-last
 dose of pola or 3 months post-last dose of rituximab for men, and 6 months post-last dose of ifosfamide, carboplatin,
 or etoposide for both women and men.

Main Exclusion Criteria

- Patients who are not hematopoietic stem cell transplant candidates.
- · Prior solid organ transplantation.
- Systemic steroid therapy or any other form of immunosuppressive therapy for lymphoma symptom control must be tapered down to ≤ 10 mg/day prednisone or equivalent. See exceptions in Section 3.2.
- Peripheral neuropathy ≥ grade 2 or demyelinating form of Charcot-Marie-Tooth disease.
- · Known active central nervous system (CNS) involvement by lymphoma, including leptomeningeal involvement.
- Active infection requiring systemic therapy.
- Other active malignancy requiring therapy. Exceptions include basal cell carcinoma of the skin or squamous cell carcinoma of the skin that has undergone potentially curative therapy or in situ cervical cancer.
- · History of severe allergic reactions attributed to compounds of similar chemical or biologic composition to study agents.
- · Recent major surgery (within 4 weeks) prior to start of protocol therapy, other than for diagnosis.
- Symptomatic cardiac disease (including symptomatic ventricular dysfunction, symptomatic coronary artery disease, and symptomatic arrhythmias), cerebrovascular event/stroke or myocardial infarction within the past 6 months.
- Known active hepatitis B virus (HBV) or hepatitis C virus (HCV) infection (See Section 3.2).
- Known active human immunodeficiency virus (HIV) infection (Section 3.2).
- History of or current progressive multifocal leukoencephalopathy (PML).
- · Females only: Pregnant or breastfeeding.

Investigational Product Dosage and Administration

The treatment plan for the Safety Lead-in and Phase 2 cohorts is as follows.

Treatment may be given on an inpatient or outpatient basis.

The maximum number of Pola-containing cycles of therapy is 6 (See Sections 5.6 and 5.7).

Note: For the drugs that are given as standard of care (i.e. R-ICE), the schedule (e.g. day of drug administration), and order of drug administration may be modified for any component of R-ICE at the investigator's discretion/ per institutional standards. In addition, dose modifications/ discontinuation of ifosfamide, carboplatin, and etoposide, whether or not they are due to toxicity are permitted at the investigator's discretion/ per institutional standards.

	SALVAGE - PolaR-ICE [‡] (Section 5.6)				
	Agent	Dose	Route	Schedule (Days within each 21- day cycle)	Maximum # Cycles
D ICE	Rituximab	375 mg/m ²	IV	Day 1	
R-ICE (Inpatient	Etoposide	100 mg/m ²	IV	Days 1-3	2-3
Schedule)**	Carboplatin	AUC 5 (750 mg max)	IV	Day 2	
Scriedule	Ifosfamide **	5000 mg/m ²	IV	Day 2	
	Polatuzumab Vedotin	Safety Lead-in: *Dose Level 1: 1.8 mg/kg Dose Level -1: 1.4 mg/kg (Section 5.4)	· IV	Day 1	2-3
	(Pola) Phase 2: Tolerable dose from Safety Lead-in (Section 5.5)	Tolerable dose from Safety Lead-in	IV	Day 1	
	CONSOLIDATION - Pola ‡‡ (Section 5.7)				

(Control of the Control of the Contr				
Agent	Dose	Route	Schedule (Days within each 21- day cycle)	Maximum # Cycles
Polatuzumab Vedotin (Pola)	1.8 mg/kg	IV	Day 1	3-4

^{*} Starting dose is Dose Level 1.

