3.1 Inclusion Criteria

- __1. Documented informed consent of the participant and/or legally authorized representative.
 - Assent, when appropriate, will be obtained per institutional guidelines
- __2. Be willing to provide archival tissue of a biopsy that was performed after the frontline systemic therapy.
 - If unavailable, exceptions may be granted with Study PI approval.

Δαρ	Criteria.	Perfor	rmance	status
Auc	CHILEHIU,	reiioi	munce	stutus

- __3. Age: ≥ 18 years
- 4. ECOG ≤ 2

Nature of Illness and Illness Related Criteria

- __5. Histologically confirmed diagnosis of diffuse large B-cell lymphoma according to the WHO classification, with hematopathology review at the participating institution. Subtypes of DLBCL including transformed indolent lymphomas (TIL), primary mediastinal large B-cell lymphoma (PMBCL), and high-grade B-cell lymphoma not otherwise specified (HGBCL-NOS) are eligible.
- __6. Biopsy-proven relapsed or refractory disease after 1 line of frontline CD20-directed immunotherapy with anthracycline- or anthracenedione-based multi-agent chemotherapy. Monotherapy with rituximab or other CD20-directed immunotherapy prior to frontline chemotherapy or as maintenance therapy, and radiation therapy in a limited field or as a part of the frontline treatment plan are permitted.
- ___7. Prior lymphoma therapy should be completed at least 2 weeks before start of protocol therapy.
- 8. Measurable disease by CT or PET/CT scan with one or more sites of disease ≥ 1.5 cm in longest dimension.
- __9. Considered eligible for high-dose chemotherapy followed by ASCT.
- __10. Fully recovered from the acute toxic effects (except alopecia) to ≤ Grade 1 to prior anti-cancer therapy.

Clinical Laboratory and Organ Function Criteria

11. Without bone marrow involvement: ANC ≥ 1,000/mm ³	ANC:	Date:
With bone marrow involvement: ANC ≥ 750/mm³		
NOTE: Growth factor is not permitted within 7 days of ANC assessment unless cytopenia is secondary to disease involvement.		
12. Without bone marrow involvement: Platelets ≥ 100,000/mm ³	Plts:	Date:
With bone marrow involvement: Platelets ≥ 75,000/mm ³		
NOTE: Platelet transfusions are not permitted within 7 days of platelet assessment unless cytopenia is secondary to disease involvement.		

Patient MRN (COH Only)	Patient Initials (F, M, L):
Institution:	

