5.13.2 Prohibited medications/ therapies

- Prohibited from **Day 1 of protocol therapy until end of protocol therapy** (last day of study agent or decision to end study agent(s) whichever occurs later).
 - Herbal and natural remedies
 - Other investigational therapy
 - Other concurrent systemic anti-cancer therapy: chemotherapy, biological response modifiers, hormone therapy, surgery, palliative radiation therapy, or immunotherapy.
- Prohibited during Salvage:
 - Strong CYP3A4 inducer or inhibitor. A washout period of 10 days is required before start of Salvage therapy.
- Exception post- Salvage but prior to Consolidation with polatuzumab vedotin:
 - Consolidation ASCT.

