10.0 STUDY CALENDAR

All assessments may increase in frequency as clinically indicated.

		Protocol therapy ^b																			
		Salvage PolaR-ICE ^C				Consolidation Pola ^d		Follow-up (~2 years)													
Protocol Activity	C1	C1 C2		(C3)		End of Salvage h	C1	C2 C3 (C4)	Safety	Active	Survival										
	Scr	D1 ^e	D1 ^e	D15 ^g	D1 ^e	D15 ^g	- 2 4.0	D1 ^e	D1 ^{e,f}	30-days post i	12 months & k	k									
Informed Consent	Х																				
Medical History	Х																				
Eligibility	Х																				
Registration	Х																				
Height	Х																				
Physical Exam	Х	x x	X		x		х	Х	Х	X											
& Vital signs ^m	_ ^					^	^	^	^	_ ^	^	^	^					,	^		
ECOG Status (Appx. A)	Х	х	х		Х		х	Х	Х	Х											
Con-med review	Х	Х	Х		Х		Х	Х	Х	Х											
AE Assessment	Х	Х	Х		Х		Х	Х	Х	Х											
Pregnancy ⁿ	Х	х	Х		Х			Х	Х												
CBC w/diff, plt & Serum chemistry ^p	хо	x	x		х		х	Х	х	x											
PT/INR and aPTT	Х																				
Correlative blood q		х	Х				Х	Х		(X)											
Correlative tumor tissue	x r		X s																		
Bone marrow biopsy/ aspirate	(X) ^u		x t																		

Protocol therapy b													
		Salvage PolaR-ICE ^C					Consolidation Pola ^d		Follow-up (~2 years)				
Protocol Activity	e Buing a C1	Screening ^a	C1	C	2	(C3)	End of Salvage h	C1	C2 C3 (C4)	Safety	Active	Survival
	Scr	D1 ^e	D1 ^e	D15 ^g	D1 ^e	D15 ^g		D1 ^e	D1 ^{e,f}	30-days post i	12 months & 24 months j	k	
PET-CT	Х			Х		Х				χV	χV		
Polatuzumab vedotin for Salvage		D1 of each cycle											
Rituximab		D1 of each cycle											
Etoposide		D1-3 of each cycle											
Carboplatin			D2 c	of each cy	/cle								
Ifosfamide (+Mesna)		D2 (Inpatient) or D1-3 (Outpatient) of each cycle											
Criteria to initiate Consolidation								Х					
Polatuzumab vedotin for Consolidation								Х	х				
Survival status												X	

- a. Screening activities to occur within 28 days prior to start of protocol therapy except for laboratory assessments and bone marrow biopsy.
- b. In the absence of treatment delay, each treatment cycle lasts 21 ± 3 days.
- c. All patients will receive 2 cycles of PolaR-ICE. Patients with PR after 2 cycles will receive an additional cycle of PolaR-ICE (3 cycles total). Patients with CR or SD after 2 cycles may receive an additional cycle of PolaR-ICE (3 cycles total) at the treating physician's discretion.

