11.2 Primary Endpoint(s)

Unacceptable Toxicity: defined as any of the following events occurring during the first 2 cycles of treatment that is at least possibly related to study treatment:

- Any Grade 3 or higher non-hematologic toxicity that does not resolve to Grade 1 or better within 7 days with the exception of:
 - Grade 3 asymptomatic laboratory abnormalities, including lipase or amylase, that are not clinically relevant, not requiring hospitalization or delay of treatment
 - Grade 4 isolated electrolyte abnormalities that are not clinically significant including, but not limited to, hypo-or hyperglycemia, hypo-or hypernatremia, hypo-or hyperkalemia, hypo-or hypermagnesemia, or hypo-or hypophosphatemia, that resolve, with or without intervention, to Grade 2 in less than 72 hours
 - Grade 3 nausea, vomiting, or fatigue controlled with supportive measures (and does not require hospitalization, TPN, or tube feeding)
 - Grade 3 infusion reaction that resolves with appropriate management to Grade 1 or better within 24 hours
 - Alopecia of any grade
- Any Grade 3 or 4 thrombocytopenia associated with clinically significant bleeding.
- Any Grade 4 neutropenia (despite the use of growth factor) or grade 4 thrombocytopenia (without clinically significant bleeding) that lasts > 21 days.
- Any Grade 4 anemia unexplained by underlying disease.
- Any treatment-related toxicity that delays cycle 2 treatment for >2 weeks.
- Any Grade 5 toxicity.

Complete response (CR) rate: defined as the proportion of response-evaluable participants (see Section 12.2) that achieve a CR after 2 cycles of PolaR-ICE therapy.

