12.2 Evaluable Participants and Participant Replacement

- Evaluable for toxicity: Patients who receive at least one dose of protocol therapy are evaluable for toxicity.
- Evaluable for unacceptable toxicity during Safety Lead-in: Patients evaluable for unacceptable toxicity (defined in Section 11.2) are:
 - 1) Those who receive the full dose of Pola, the full doses of rituximab and carboplatin, and at least 67% of the doses of etoposide and ifosfamide during the first 2 cycles of Salvage, OR
 - 2) Those who experience any unacceptable toxicity during the first 2 cycles of Salvage regardless of actual dose of protocol therapy received.

During safety lead-in, patients who are not evaluable for unacceptable toxicities will be replaced.

• Evaluable for response during Phase 2:

Evaluable patients are defined as eligible participants who have received at least one cycle of PolaR-ICE salvage therapy and have at least one disease evaluation post-baseline.

Patients will be evaluable and be considered non-CR in the primary response evaluation if they discontinued study therapy prior to having a response assessment after 2 cycles of PolaR-ICE because of progressive disease or unacceptable toxicity (rather than due to withdrawal of consent or investigator decision). If a patient discontinues study treatment prior to the first response assessment after 2 cycles of PolaR-ICE due to progressive disease, the treating physician is encouraged to obtain imaging to confirm progression.

During Phase 2 enrollment, participants who are not evaluable for response will be replaced and excluded from Phase 2 efficacy analyses, but will be included in the general toxicity analyses if they receive any protocol treatment.

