APPENDIX B: LYMPHOMA RESPONSE CRITERIA [38]

Response	Site	CT-Based Response	PET-CT Based Response
Complete Response		Complete radiologic response (all of the following)	Complete metabolic response (even with a persistent mass)
	Lymph nodes and extralymphatic sites	Target nodes/nodal masses must regress to ≤1.5 cm in longest diameter (LDi). No extralymphatic sites of disease.	Score ≤ 3* with or without a residual mass on 5-point scale†. It is recognized that in Waldeyer's ring or extranodal sites with high physiologic uptake or with activation within spleen or marrow (e.g., with chemotherapy or myeloid colony-stimulating factors), uptake may be greater than normal mediastinum and/or liver. In this circumstance, complete metabolic response may be inferred if uptake at sites of initial involvement is no greater than surrounding normal tissue even if the tissue has high physiologic uptake.
	Nonmeasured lesion	Absent	Not applicable
	Organ enlargement	Regress to normal	Not applicable
	New lesions	None	None
	Bone marrow	Normal by morphology; if indeterminate, IHC negative	No evidence of FDG-avid disease in marrow
Partial		Partial remission (all of the following)	Partial metabolic response
Response	Lymph nodes and extralymphatic sites	≥ 50% decrease in SPD of up to 6 target measurable nodes and extranodal sites When a lesion is too small to measure on CT, assign 5 mm X 5 mm as the default value When no longer visible, 0 X 0 mm For a node > 5 mm X 5 mm, but smaller than normal, use actual measurement for calculation	Score 4 or 5† with reduced uptake compared with baseline and residual mass(es) of any size At interim, these findings suggest responding disease At end of treatment, these findings indicate residual disease

Response	Site CT-Based Response		PET-CT Based Response			
	Nonmeasured lesion	Absent/normal, regressed, but no increase	Not applicable			
	Organ enlargement	Spleen must have regressed by > 50% in length beyond normal	Not applicable			
	New lesions	None	None			
Bone marrow Not applicable		Residual uptake higher than uptake in normal marrow but reduced compared with baseline (diffuse uptake compatible with reactive changes from chemotherapy allowed). If there are persistent focal changes in the marrow in the context of a nodal response, consideration should be given to further evaluation with MRI or biopsy or an interval scan				
No response		Stable disease	No metabolic response			

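### Eligibility does not exclude a patient whose only measurable site was irradiated shortly before entry, so a radiation-induced CR could count toward the primary endpoint

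*Combined protocol and SAP*

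**What the plan says.** The entry rules are in the Synopsis and Section 3.1.

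- **Criterion 6**, after requiring biopsy-proven relapsed or refractory disease following one frontline line, adds that "radiation therapy in a limited field or as a part of the frontline treatment plan are permitted".
- **Criterion 7:** "Prior lymphoma therapy should be completed at least 2 weeks before start of protocol therapy". Radiation has no separate washout.
- **Criterion 8:** "Measurable disease by CT or PET/CT scan with one or more sites of disease ≥ 1.5 cm in longest dimension". It does not say whether an irradiated site qualifies.
- **Section 10.0, footnote a:** "Screening activities to occur within 28 days prior to start of protocol therapy except for laboratory assessments and bone marrow biopsy". PET-CT is not among the exceptions, so the baseline scan may be up to 28 days old.
- **Section 5.13.2** lists "hormone therapy, surgery, palliative radiation therapy, or immunotherapy" among the concurrent anti-cancer treatments barred from Day 1 until protocol therapy ends.

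The primary endpoint in Section 11.2 is the proportion of response-evaluable participants "that achieve a CR after 2 cycles of PolaR-ICE therapy". Section 12.2 defines the evaluable set as "eligible participants who have received at least one cycle of PolaR-ICE salvage therapy and have at least one disease evaluation post-baseline", plus certain early discontinuations that count as non-CR. In Appendix B, PET-CT CR is a score of 3 or less "with or without a residual mass on 5-point scale".

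No rule for previously irradiated lesions appears in Section 3.2, 11.1, 11.2, 12.2, 12.6 or Appendix B.

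**The concern.** In criterion 6, the word 'or' separates limited-field radiation from radiation that belonged to the frontline plan. Nothing else says when the limited-field radiation may have been given or to which site. A patient irradiated between relapse and entry therefore meets the criterion as written.

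If the irradiated site is the only measurable disease, PET-CT after two cycles cannot separate the effect of PolaR-ICE from that of radiation completed a few weeks earlier. The trial has no control arm in which such an effect would also appear. Section 12.1.2 rests the decision on a count, at least 21 CRs of 40 against a 40% null, and a radiation-induced CR enters that count in full. It can only add to the CR count, and so favours declaring the regimen worthy of further study.

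**Working it through.** **1. Timing.** Let Day 1 be the start of protocol therapy. The baseline PET-CT may be up to 28 days before it, and prior lymphoma therapy must end at least 14 days before it. Since 28 − 14 = 14, there is a stretch of up to two weeks in which radiation can follow the baseline scan and still satisfy criterion 7. In that case the site qualifies under criterion 8 on a scan taken before it was irradiated. If the scan follows radiation, the site still qualifies when it measures at least 1.5 cm, with no need to show progression since.

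**2. The plan's own figures.** Inputs from Section 12.1.2: stage 1 has 20 patients and stops if there are fewer than 8 CRs; stage 2 adds 20; success is at least 21 CRs of 40; null 40%, alternative 60%. With X1 and X2 the CR counts in the two stages, each Binomial(20, p):

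P(success) = sum over x = 8 to 20 of P(X1 = x) × P(X2 ≥ 21 − x)

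| Quantity | Computed | Stated |
|---|---|---|
| Type I error (p = 0.40) | 0.0731 | 7.3% |
| Power (p = 0.60) | 0.8659 | 87% |
| Early stop, P(X1 ≤ 7), p = 0.40 | 0.4159 | 42% |
| Expected N, 20 + 20 × (1 − 0.4159) | 31.68 | 31.7 |

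All four reproduce. The design calculation is not in question.

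**3. Effect of affected patients.** The documents give neither the number of such patients nor their CR chance, so both are assumptions. Suppose k of the 40 have a sole, recently irradiated site and CR chance q, while the other 40 − k have the null rate of 40%. If k1 and k2 of them fall in stages 1 and 2:

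X1 = Binomial(20 − k1, 0.40) + Binomial(k1, q), and X2 = Binomial(20 − k2, 0.40) + Binomial(k2, q)

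The success formula is unchanged. Even k is split equally between stages; for k = 1 the range covers either stage.

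| k of 40 | q = 60% | q = 80% |
|---|---|---|
| 0 | 7.3% | 7.3% |
| 1 | about 8.2% | 9.1-9.2% |
| 2 | 9.2% | 11.3% |
| 4 | 11.5% | 16.8% |

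As an extreme, with q = 100% the figures are 13.6% for k = 2 and 23.3% for k = 4. At the low end, one patient with q = 50% gives about 7.8%.

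**The case against.** **Permission to irradiate relapsed disease.** A reader might infer that the protocol expressly allows this. It does not say so. Criterion 6 lists prior treatment compatible with one frontline line. Limited-field radiation there could refer to earlier indolent disease, since transformed lymphoma is eligible. What stands is that radiation at relapse is not excluded and that five centers must apply the criterion alike.

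**Such CRs will be counted.** A reader might also infer that radiation-induced CRs are certain to enter the result. That needs a chain of events: radiation after relapse and before entry, a qualifying site at screening, and no other site that decides the response. Appendix B requires every site to clear, with no new lesions and no FDG-avid marrow disease. Section 11.1 adds a confirmatory marrow biopsy where the marrow was involved at baseline. Radiation to one of several active sites cannot by itself produce a CR. The point is therefore conditional.

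**Scan before radiation.** This case is narrow: the scan must be early in the window and radiation must start and finish by 14 days before Day 1. Section 3.0 requires criteria to be met on screening examination. The written windows still permit it.

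**Inconsistency with Section 5.13.2.** One might read the ban on palliative radiation from Day 1 as showing that the plan overlooks radiation before Day 1. It does not overlook it: criterion 7 is the pre-treatment counterpart. No figure in the documents shows that 2 weeks is too short, so no claim is made on that.

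**The benchmark.** The 40% null comes from a cited randomized study. If that study admitted similar patients, part of the effect is already in the null. The documents do not say. A net bias against 40% therefore cannot be established from them, and the table assumes that the null contains no such patients.

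**Visibility.** Section 12.6 will summarise prior treatment, so prior radiation should be visible descriptively. That does not change how a CR is counted.

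**Conclusion.** The gap is real, and no other section closes it. As written, the criteria let in a patient whose sole measurable site was irradiated shortly before entry, and a CR at that site would count toward the 21 of 40. How much this matters depends wholly on assumed inputs: from under one percentage point of type I error (one patient, 50% or 60% CR chance on the rounded figures) to about 9.5 points (16.8% − 7.3%, four patients at 80%). The larger figure needs 10% of the trial to be such patients with double the null CR chance, and nothing in the documents suggests that this will occur. The sample size, type I error and power as stated are correct. This is a cheap improvement to eligibility wording, worth making because a single-arm count has no other protection against this bias.

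**What to change.** In criterion 8, in both the Synopsis and Section 3.1, require at least one measurable site that either has not been irradiated since frontline therapy or has documented progression after radiation. Also require that the baseline PET-CT used for response follow the end of any pre-entry radiation.

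If enrolment can no longer change, add one sensitivity analysis to Section 12.6 instead. It would count as non-CR any CR in a patient whose only disease was irradiated after relapse without documented progression afterwards. This needs radiation sites and dates to be recorded. The analysis should not reclassify patients whose irradiated site had progressed, because the eligibility rule above accepts that site as valid.

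**Cost.** One or two sentences. A few single-site patients become ineligible, and an occasional patient scanned before radiation needs the scan re-timed or repeated. The sample size, decision rule, type I error and power stay as planned.
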